## **Appendix B. Potential medication interactions with magnesium citrate**

Magnesium containing drugs can potentially lower drug levels of some medications. We will advise treating physicians to allow there be a 6-hour window between administration of these drugs and magnesium citrate. This should not restrict the enrollment of someone taking these drugs. Here is a list of drugs that can be affected by magnesium citrate:

Demeclocycline  
Dolutegravir  
Doxycycline  
Eltrombopag  
Lymecycline  
Minocycline  
Oxytetracycline  
Potassium Phosphates, Intravenously  
Tetracycline  
Ciprofloxacin  
Deflazacort  
Fleroxacin  
Gemifloxacin  
Levofloxacin  
Moxifloxacin  
Norfloxacin  
Ofloxacin  
Penicillamine  
Sodium Phosphates, Intravenously  
Vitamin D

## Appendix C: Adverse Event Reporting and Unanticipated Events

As noted in section 11, investigators will report all “serious adverse events,” defined as adverse events that are serious and have a reasonable possibility that the event was due to a study drug or procedure (or of uncertain relatedness), to the CCC within 24 hours. The CCC will then notify the NHLBI and Central Institutional Review Board (cIRB).

The Medical Monitor at the CCC will work collaboratively with the reporting investigator to determine if a serious adverse event has a reasonable possibility of having been caused by the study drug or study procedure, as outlined in 21 CFR 312.32(a)(1), and below. The Medical Monitor will be unblinded and will also determine if the event is unexpected for magnesium citrate or the probiotic Floranex. An adverse is considered “unexpected” if it is not listed in the investigator brochure or the study protocol (21 CFR 312.32(a)). If a determination is made that a serious adverse event has a reasonable possibility of having been caused by a study procedure or the study drug, it will be classified as a suspected adverse reaction. If the suspected adverse reaction is unexpected, it will be classified as a serious unexpected suspected adverse reaction (SUSAR).

The CCC will report all unexpected deaths, serious and treatment related adverse events, and SUSARs to the DSMB, NHLBI, and cIRB within 7 days after receipt of the report from a clinical site. A written report will be sent to the NHLBI, DSMB, FDA, and the cIRB within 15 calendar days. The DSMB will also review all reported adverse events and clinical outcomes during scheduled interim analyses. The CCC will distribute the written summary of the DSMB’s periodic review of reported adverse events to the cIRB in accordance with NIH guidelines (<http://grants.nih.gov/grants/guide/notice-files/not99-107.html>). The Medical Monitor will provide to Sandoz Pharmacovigilance any significant safety findings (without disclosing protected health information) during the conduct of the trial.

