## **2.3 Study Design**

We will conduct an investigator-initiated, single center, blinded, placebo-controlled, randomized clinical trial evaluating magnesium citrate plus the probiotic Floranex for the treatment of adults hospitalized with COVID-19. Patients, treating clinicians, and study personnel will all be blinded to study group assignment.

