### **3.7 Randomization and Blinding**

Participants confirmed to meet all eligibility criteria who have provided informed consent will be randomized 1:1 to magnesium citrate plus a the probiotic Floranex versus placebo. A randomization code will be provided to the site investigator or delegate from a centralized, web-based platform. Randomization will require provision of the screening number and confirmation of patient eligibility.

Randomization will be completed in permuted blocks of varying size and stratified by site. The randomized sequence allocation will be stored on a secure server and will not be available to site study personnel. Site research personnel will have a unique Personal Identification Number (PIN) to access the randomization system. Each subject will receive a computer-generated randomization ID number. The computer-generated randomization ID number will be provided to the pharmacy who will provide a dose pack containing magnesium citrate plus a the probiotic Floranex or placebo. The participant, treating clinicians, study personnel, and outcome assessors will all remain blinded to group assignment until after the database is locked and blinded analysis is completed.

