## **4.4 Co-Interventions**

This trial will control the use of magnesium citrate plus the probiotic Floranex vs placebo during the intervention period. Enrolled participants will not receive open-label magnesium citrate or the probiotic Floranex during the intervention period. All other treatment decisions will be made by treating clinicians without influence from the protocol. Administration of other antiviral medications (“rescue therapy”) will be allowed. The decision to administer other antiviral medications will be made by treating clinicians and will be recorded in the case report form. The decision to administer immunomodulating medications, including corticosteroids, will be made by treating clinicians and will be recorded in the case report from.

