## **4.6 Criteria for Stopping Study Drug**

Administration of the blinded study drug may be stopped temporarily or permanently for (a) adverse events, (b) results of on-study monitoring, (c) clinical deterioration, or (d) evidence of an alternative cause to the patient’s symptoms.

If a patient experiences an adverse event that the patient (or legally authorized representative), treating clinicians, or investigators feel merits temporarily or permanently stopping the study drug, the study drug will be stopped.

The explanation for stopping the study drug will be recorded in the case report form, and the adverse event will be recorded and reported according to the adverse event guidelines below. If the adverse event resolves to the extent that the patient (or legally authorized representative), treating clinicians, and investigators feel that resuming the

study drug is appropriate, the study drug will be resumed, and this information will be recorded in the case report form.

Patients on study may experience clinical deterioration due to their illness. Clinical deterioration will be defined as a decrease of 1 point or more on the ordinal scale for the primary outcome (e.g., patient transitions from “hospitalized on supplemental oxygen” to “hospitalized on non-invasive ventilation or high flow nasal cannula”). Patients who experience clinical deterioration in either group may be administered other antivirals or immunomodulators as “rescue therapy”. For patients who experience clinical deterioration for which treating clinicians feel optimal care would be to stop the study drug, unblind group assignment, and administer magnesium citrate and/or the probiotic Floranex to patients in the placebo group, the study drug will be stopped, the site investigator will contact the coordinating center to receive the unblinded study group assignment, and any additional treatment will be deferred to treating clinicians. In this situation, the following data will be recorded in the case report form: the criteria met for clinical deterioration; the reason for stopping study drug and unblinding; use of magnesium citrate, other antivirals, and immunomodulators; and study outcomes.

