## 11.2 Safety Monitoring

Assuring patient safety is an essential component of this protocol. Each participating investigator has primary responsibility for the safety of the individual participants under his or her care. The Investigators will determine daily if any adverse events occur during the period from enrollment through **study day 7** or hospital discharge, whichever occurs first and will determine if such adverse events are reportable. Thereafter, adverse events are not required to be reported unless the investigator feels the adverse event was related to study drug or study procedures.

The following adverse events will be considered reportable and thus collected in the adverse event case report forms:

- Serious adverse events
- Non-serious adverse events that are considered by the investigator to be related to study procedures or of uncertain relationship (Appendix C)
- Events leading to permanent discontinuation of study drug

Study-specific clinical outcomes (Primary, Secondary and Safety Outcomes and Assessments During the Study), including serious outcomes such as organ failures and death, are systematically recorded in the case report forms and are exempt from adverse event reporting unless the investigator deems the event to be related to the administration of study drug or the conduct of study procedures (or of uncertain relationship) as outlined in Appendix C.

After randomization, adverse events must be evaluated by the investigator. If the adverse event is judged to be reportable, as outlined above, then the investigator will report to the Clinical Coordinating Center (CCC) their assessment of the potential relatedness of each adverse event to the study drug or protocol procedure via electronic data entry. Investigators will assess if there is a reasonable possibility that the study procedure caused the event, based on the criteria outlined in Appendix C. Investigators will also consider if the event is unexpected. Unexpected adverse events are events not listed in the study protocol and the package insert for the study drugs will also determine if adverse events are unanticipated given the patient's clinical course, previous medical conditions, and concomitant medications.

If a patient's treatment is discontinued as a result of an adverse event, study site personnel must also report the circumstances and data leading to discontinuation of treatment in the adverse event case report forms.

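### Serious adverse event causality is decided jointly by the investigator and an unblinded Medical Monitor, and nothing fixes the investigator's blinded grade first

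*Combined protocol and SAP*

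**What the plan says.** Two sections promise blinding without exceptions. Section 2.3: "Patients, treating clinicians, and study personnel will all be blinded to study group assignment". Section 3.7: "The participant, treating clinicians, study personnel, and outcome assessors will all remain blinded to group assignment until after the database is locked". Section 7.1 adds that investigators stay blinded while the DSMB decides whether to continue after 30 participants.

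The investigator grades relatedness. Section 11.2: "Investigators will assess if there is a reasonable possibility that the study procedure caused the event, based on the criteria outlined in Appendix C". That assessment goes to the Clinical Coordinating Center (CCC) by electronic entry, and C.2 gives the grading categories.

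For serious events, Appendix C adds a second decider: "The Medical Monitor at the CCC will work collaboratively with the reporting investigator to determine if a serious adverse event has a reasonable possibility". The next sentence settles that person's blinding status: "The Medical Monitor will be unblinded and will also determine if the event is unexpected for magnesium citrate or the probiotic Floranex".

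Section 4.6 provides a code break for a deteriorating patient whose treating clinicians want to stop the study drug and unblind. In that case, "the site investigator will contact the coordinating center to receive the unblinded study group assignment".

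**The concern.** Whether an adverse event is related to treatment is a judgement, and blinding is what keeps it even-handed between arms. Under Appendix C one of the two people making it knows the allocation. For a placebo patient the Monitor knows that neither active product can be the cause; for an active patient the Monitor knows that they can. The same clinical picture can then be classified differently by arm.

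There is a second path. An investigator who discusses causality with someone who knows the arm may infer the arm from the position taken. The same investigator role reviews adverse events daily under 11.2.

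At stake are the classification of serious events, the expedited reports built on it, and the blinding of the people who grade later events.

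**Working it through.** No arithmetic decides this point. The check is to list each safety decision, who makes it, and whether that person knows the arm.

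| Decision | Who decides | Knows the arm? |
|---|---|---|
| Relatedness grade sent to the CCC | Investigator (11.2, C.2) | Not by design |
| 24-hour alert to the CCC | Investigator or site staff (11.3, Appendix C) | Not by design |
| Exemption of study-specific outcomes; recording of non-serious events | Investigator (11.2, C.3) | Not by design |
| Collection of serious events to discharge | Independent of causality opinion (11.3) | Not applicable |
| Whether a serious event is a suspected adverse reaction | Investigator with Medical Monitor (Appendix C) | One of the two does |
| Whether the event is unexpected, and so a SUSAR | Medical Monitor (Appendix C) | Yes |
| 7-day and 15-day reports | CCC, largely following the two rows above | Depends on them |

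1. The unblinded judgement enters at the fifth row. Expectedness alone would not disturb the investigator's grade. The weak point is the shared causality decision.

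2. The investigator's grade exists before or alongside that discussion, since 11.2 sends it to the CCC. No section says that it is locked, that it survives the joint decision, which opinion prevails if the two differ, or that the Monitor must withhold the arm.

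3. The gates in the first three rows are the investigator's. For study-specific outcomes, 11.2 says that they "are exempt from adverse event reporting unless the investigator deems the event to be related to the administration of study drug". These gates are affected only if the investigator has learned the arm.

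4. Section 4.6 is one way to learn it, for one patient at a time. The site investigator receives the assignment, investigators assess adverse events daily through Day 7 or discharge (11.2), and no text passes that patient's later grading or Day 7 scoring to someone still blinded. Section 3.7 lists no exception for this.

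5. Scale. Section 7.1 plans 15 patients per arm. One patient moved into or out of a related-event count changes that arm's proportion by 1/15 = 0.067, or 6.7 percentage points. This is the unit of change, not an estimate of bias: the documents give no rate of serious events, of joint reviews or of code breaks.

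6. A separate inconsistency appears in the same passages. Section 4.4 says: "Enrolled participants will not receive open-label magnesium citrate or the probiotic Floranex during the intervention period". Sections 4.6 and 9.1.3 allow open-label product after clinical deterioration. Section 4.4 has no exception, and the intervention period is not defined.

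**The case against.** A reader might infer that related-event counts are biased by construction, with placebo events judged unrelated and then lost through the C.3 exemption. The documents do not support this. That exemption, the 24-hour alert and the recording of non-serious events rest with the investigator. Serious events are collected to discharge whatever the causality opinion. Safety outcomes are collected systematically in both arms, and the DSMB reviews all reported events and clinical outcomes at interim analyses. No comparison of related events by arm is specified. Causality also covers study procedures, so knowing that a patient is on placebo does not force a finding of unrelated.

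A reader might also infer that 4.6 gives the investigator the randomization code. It gives one patient's assignment, after deterioration, at the treating clinicians' wish, with the reasons recorded. As a specific exception to 3.7 it mainly needs a cross-reference. Any effect on Day 7 scoring is a possibility only, because the documents do not say that the unblinded investigator scores that patient.

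The conflict with 2.3 and 3.7 can be questioned too. The term for study personnel is undefined and may not cover a Monitor at the coordinating center, and nothing says that the Monitor discloses the arm. Section 3.7 does use a narrower term for site staff, which favors a wider reading of the general one. In any case the investigator is covered, and no rule protects the investigator from learning the arm in the joint discussion.

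These limits stand and define the point's reach. They do not answer the central gap: Appendix C prescribes a shared causality decision with an unblinded person and sets no order or firewall.

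**Conclusion.** The point holds in a limited form. Following Appendix C as written, suspected-reaction and SUSAR classification, and the expedited reports that turn on them, can depend on the arm, and the investigator may learn the arm in the process. Initial reporting, the C.3 exemption and the grading of later events are affected only if that happens or after a 4.6 code break. Collection of serious events under 11.3 does not turn on the causality opinion.

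The joint decision does not enter the primary analysis. The primary outcome could be touched only if someone who has learned the arm also scores Day 7, and the documents leave that open.

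The size is unknown. The conclusion assumes that the joint determination can override or shape the investigator's submitted grade, which the text permits but does not spell out. The reading that 2.3 and 3.7 are contradicted by the Monitor's own status further assumes that the Monitor counts as study personnel; the risk to the investigator's blinding does not need that assumption.

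**What to change.** - **Appendix C:** require the blinded investigator to enter and lock the causality grade before any contact with the Medical Monitor. Name that grade as the one used in any summary of related events by arm.
- **Appendix C:** limit the unblinded Monitor to expectedness and regulatory classification. Store any separate causality opinion from the Monitor apart from the site's data, and do not return it to the site.
- **Sections 2.3 and 3.7:** state the exceptions to blinding for the Medical Monitor and for the 4.6 code break.
- **After a code break:** where the existing team allows, have a member who is still blinded grade later events and score Day 7 for that patient.
- **Sections 4.4, 4.6 and 9.1.3:** the sponsor must reconcile these passages on open-label product. This is separate from causality, and which rule applies is the sponsor's decision.

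The cost is protocol wording and one database field. The reassignment after a code break depends on a blinded colleague being available, which the documents do not establish. The downside is that two causality opinions may differ, and both must then be kept.

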### C.1. Unanticipated Problems (UP)

Investigators must also report Unanticipated Problems, regardless of severity, associated with study procedures within 24 hours. An unanticipated problem is defined as follows: any incident, experience, or outcome that meets all of the following criteria:

- Unexpected, in terms of nature, severity, or frequency, given the research procedures that are described in the protocol-related documents, such as the IRB-approved research protocol and informed consent document; and the characteristics of the subject population being studied;
- Related or possibly related to participation in the research, in this guidance document, possibly related means there is a reasonable possibility that the incident, experience, or outcome may have been caused by the procedures involved in the research;
- Suggests that the research places subjects or others at a greater risk of harm (including physical, psychological, economic, or social harm) than was previously known or recognized.

### C.2. Determining Relationship of Adverse Events to Study Drug or Study Procedures

Investigators will be asked to grade the strength of the relationship of an adverse event to study drug or study procedures as follows:

- Definitely Related: The event follows: a) A reasonable, temporal sequence from a study procedure; and b) Cannot be explained by the known characteristics of the patient’s clinical state or other therapies; and c) Evaluation of the patient’s clinical state indicates to the investigator that the experience is definitely related to study procedures.
- Probably or Possibly Related: The event should be assessed following the same criteria for “Definitely Associated”. If in the investigator’s opinion at least one or more of the criteria are not present, then “probably” or “possibly” associated should be selected.

- Probably Not Related: The event occurred while the patient was on the study but can reasonably be explained by the known characteristics of the patient's clinical state or other therapies.
- Definitely Not Related: The event is definitely produced by the patient's clinical state or by other modes of therapy administered to the patient.
- Uncertain Relationship: The event does not meet any of the criteria previously outlined.

[figure not shown]
### **C.3. Clinical Outcomes that may be Exempt from Adverse Event Reporting**

Study-specific outcomes of acute respiratory infection, COVID-19, and critical illness will be systematically collected for all patients in both study group and are exempt from adverse event reporting unless the investigator considers the event to be Definitely or Possibly Related (or of an Uncertain Relationship) to the study drug or study procedures. Examples of study-specific clinical outcomes include:

- Death not related to the study procedures
- Neurological events
  - Seizure
- Cardiovascular events
  - Receipt of vasopressors
  - Atrial or ventricular arrhythmia
  - Cardiac arrest
- Respiratory events
  - Hypoxemia requiring supplemental oxygen
  - Acute respiratory distress syndrome
  - Receipt of mechanical ventilation
  - Receipt of extra-corporeal membrane oxygenation
- Gastrointestinal events
  - Elevation of aspartate aminotransferase or alanine aminotransferase
  - Acute pancreatitis
- Renal events
  - Acute kidney injury
  - Receipt of renal replacement therapy
- Endocrine events
  - Symptomatic hypoglycemia
- Hematologic or coagulation events
  - Neutropenia, lymphopenia, anemia, or thrombocytopenia
- Dermatologic events
  - Severe dermatologic reaction (e.g., Steven's Johnson Syndrome)

Note: A study-specific clinical outcome may also qualify as a reportable adverse event. For example, a ventricular arrhythmia that the investigator considers Definitely or Possibly Related to the study drug would be both recorded as a study-specific clinical outcome and reported as a Serious and Definitely or Possibly Related Adverse Event.

## Appendix E

### COVID Ordinal Outcome Scale

Patient State	Descriptor	Score
Uninfected	Uninfected, no viral RNA detected	0
Ambulatory Mild Disease	Asymptomatic, viral RNA detected	1
	Symptomatic, independent	2
	Symptomatic, assistance needed	3
Hospitalized Moderate Disease	Hospitalized, no oxygen needed	4
	Hospitalized, oxygen by mask or nasal prongs	5
Hospitalized Severe Disease	Hospitalized, oxygen by NIV or high flow	6
	Intubation and mechanical ventilation, $pO_2/FiO_2 \geq 150$ or $SpO_2/FiO_2 \geq 200$	7
	Mechanical ventilation, $pO_2/FiO_2 < 150$ ( $SpO_2/FiO_2 < 200$ ) or vasopressors	8
	Mechanical ventilation, $pO_2/FiO_2 < 150$ and vasopressors, dialysis or ECMO	9
Dead	Dead	10
